#### 2.3. Exploratory Objectives and Outcomes

The exploratory objectives are to compare change from baseline to the 2-year follow-up (including all follow-ups) between the groups in a range of outcomes. These outcomes will only be exploratory and/or hypothesis generating, which is why multiplicity is not considered to be a problem and not statistically corrected for.

These outcomes are:

1) Weight change in percent (from baseline to 3 and 12 months follow-up).

2) Change in physical activity level a. physical activity level b. intensity c. exercise sessions per week d. hours being physically active per week (based upon questions in baseline questionnaire: Kind of activity / number of sessions a week / total hours a week and questions in 2-years questionnaire: How often / how intense / how long sessions) (from baseline to 24

months follow-up).

3) Pain intensity on a 100 mm VAS with terminal descriptors of 'no pain' (0) and 'worst pain possible' (100) (from baseline to 3 and 12 months follow-up).

Further exploratory objectives may be added later on.

## 2.4. Descriptive Assessments

Baseline characteristics will be presented in a table (Table 2).

Furthermore, the following treatment-related variables will be presented descriptively:

- Compliance with exercise during the 12 weeks is recorded from the patients exercise diary notes. The patients were instructed to complete two to three exercise sessions a week over twelve weeks (24-36 sessions). Compliance is assessed as the total number of exercise sessions completed out of the minimum of 24 sessions. *Excellent compliance* is defined as participation in 24 or more sessions (more than 100 %), *satisfactory compliance* is defined as 19-23 sessions (80-100 %) and *poor compliance* is defined as 18 or less sessions (less than 80 %). Less than 80 % compliance is defined as not completed treatment allocation.
- 2) Pain level during the 12 weeks exercise treatment is recorded from the patients exercise diary notes where they have reported pain on a visual analogue scale (VAS) during and after each training session.
- Satisfaction with the treatment effect will be registered at each follow-up until 12 months on a five-point Likert scale (very dissatisfied, dissatisfied, neither satisfied nor dissatisfied, satisfied, very satisfied).
- 4) Patients crossing over from the exercise group to arthroscopy and patients in both groups going through additional surgeries during the 24 months follow-up period will be registered (Table 3).
- 5) Patients crossing over from the arthroscopy group to exercise, not have had postoperative active physiotherapy (exercises) more than 80 % of twice a week in 12 weeks (19 or more sessions)(equivalent to 80 % in the exercise group).
- 6) Adverse events (AE) and seriously adverse events (SAE) will be registered and categorized into index knee or sites other than index knee. The project workers will record any adverse events that the participant experiences or tells them about and at all follow-ups all participants are asked about potential adverse events. For all participants in both groups including all patients crossing over (see section 2.7.1.) to the other intervention a project worker will look through hospital records to register if any pre-defined perioperative or postoperative adverse events occurred, or adverse events related to the exercise therapy (Table 1).

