# 2.7.2. Secondary Endpoints

Secondary endpoints will be analyzed for between- and within-group differences using ITT, PP (per protocol) and AT (as treated) analyses (see sections 2.7.1 and 5.2.)(Figure 2).

The *PP population* will be defined as the following:

In the arthroscopy group, included patients are: All patients randomized to arthroscopy that went through surgery, and not have had postoperative active physiotherapy (exercises) more than 80 % of twice a week in 12 weeks (19 or more sessions)(equivalent to 80 % in the exercise group), are included.

In the exercise group patients who participated in the program with at least 80 % compliance during the 12 weeks intervention period and did not cross over to the surgical treatment arm during the 2 years period and not have had any other surgery to the index knee (osteotomy, arthroplasty) within two years, are included.

This means that the following will be excluded from the PP analysis:

- 1) Those who were randomized to arthroscopy
  - a. but never went through surgery
  - b. but had postoperative exercise therapy supervised by physiotherapists (defined as 19 or more sessions )
- 2) Those who were randomized to exercise therapy supervised by physiotherapist
  - a. but never went through exercise or participated in less than 19 sessions ( 80 % of the minimum of 24 exercise sessions)
  - b. but crossed over to the surgical treatment arm within 2 years

The AT population will be defined as the following:

In the arthroscopy group, included patients are: All patients randomized to arthroscopy that went through surgery, and not have had postoperative active physiotherapy (exercises) more than 80 % of twice a week in 12 weeks (19 or more sessions)(equivalent to 80 % in the exercise group), are included. Additionally; Patients from the exercise group that within 2 years crossed over to surgery, are included in the arthroscopy group.

In the exercise group patients who participated in the program with at least 80 % compliance

during the 12 weeks intervention period and did not cross over to the surgical treatment arm during the 2 years period and not have had any other surgery to the index knee (osteotomy, arthroplasty) within two years, are included. Additionally; patients from the arthroscopy group that within two years crossed over to exercise (performed more than 80 % of twice a week in 12 weeks (19 or more sessions), are included in the exercise group.

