## 4. Study Population

#### 4.1. Subject Disposition

Study procedures, including recruitment strategies and inclusion and exclusion criteria, have been described in the PhD protocol (Appendix 1). Patients included in the trial were randomized to: A) Exercise therapy or B) Arthroscopic partial meniscal resection. All consecutive patients who came to the two inclusion sites on the days of the orthopedic surgeons outpatient clinic fulfilling the eligibility criteria were asked to enter the study. Patients fulfilling all eligibility criteria, but refusing to participate in the randomization, were registered.

Crossovers are a common problem in studies randomizing to surgical or non-surgical treatments. In this study participants who experienced impairment of their symptoms or lack of improvement during the 2-year observation period, were reassessed at any time when necessary by the orthopedic surgeon who was responsible for the study. Indication for surgery (crossing over from exercise to arthroscopy) or re-operation (meniscal re-resection or other surgery in the index knee within 2 years) was based upon patient's history, clinical and radiological examinations.

Patients from the arthroscopy group that had postoperative active exercise therapy supervised by a physiotherapist more than 80 % of twice a week in 12 weeks (19 or more sessions)(equivalent to 80 % in the exercise group) were regarded as crossing over to the exercise group.

The frequency of crossovers from exercise to arthroscopy and vice versa, re-operations with meniscal re-resections or other surgery in the index knee within 2 years will be registered and reported (Table 3).

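### Section 2.4 item 5 reverses the arthroscopy-to-exercise crossover definition, and the compliance percentages do not match the session counts they label

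*SAP*

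**What the plan says.** **Compliance (SAP 2.4).** The denominator is fixed: "Compliance is assessed as the total number of exercise sessions completed out of the minimum of 24 sessions". The top band is "Excellent compliance* is defined as participation in 24 or more sessions (more than 100" per cent), and the lower two are "satisfactory compliance* is defined as 19-23 sessions (80-100 %) and *poor compliance* is defined as 18 or less sessions (less than 80" per cent). The section adds a rule given only as a percentage: "Less than 80 % compliance is defined as not completed treatment allocation". Table 3 repeats the bands as percentages without counts.

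**Crossover from arthroscopy to exercise.** Section 2.4 item 5 reads "Patients crossing over from the arthroscopy group to exercise, not have had postoperative active physiotherapy (exercises) more than 80 % of twice a week in 12"; the SAP glosses this amount as 19 or more sessions. Section 4.1 takes arthroscopy patients who had that amount of supervised exercise and says they "were regarded as crossing over to the exercise group". The as-treated definition in 2.7.2 also moves patients who performed 19 or more sessions into the exercise group.

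**Analysis populations (2.7.2).** For the per-protocol and as-treated sets, exercise-arm inclusion is worded as at least 80% compliance. The list of per-protocol exclusions that follows gives a count: those who never exercised or "participated in less than 19 sessions ( 80 % of the minimum of 24 exercise sessions". The legend to Figure 2 also gives 19 sessions as the cut-off.

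**The concern.** There are two separate problems.

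The first is a reversed rule. Item 5 describes as crossovers the patients who stayed below the threshold; sections 4.1 and 2.7.2 describe those who reached it. Two outputs depend on crossover status: the arthroscopy-to-exercise rows of Table 3, and the adverse-event grouping in 2.7.2, which lists patients randomized to surgery who crossed to exercise among the exercise-therapy groups. Item 6 of section 2.4 refers to 2.7.1 for crossing over, but 2.7.1 contains no crossover definition that would settle the matter.

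The second is a mismatch between percentages and counts. Where the plan gives a percentage alone, a programmer applying it to a denominator of 24 gets a different answer from the count at two values: 19 and 24 sessions. The value 19 decides treatment completion and per-protocol or as-treated membership. The value 24 decides only which descriptive band a patient falls in.

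Section 7 makes the SAP the work description for a statistician working on blinded data, so each definition should be executable as written.

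**Working it through.** **1. The crossover definitions side by side**

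| Place in SAP | Arthroscopy patient with 19 or more postoperative sessions | Arthroscopy patient with 18 or fewer |
|---|---|---|
| 2.4 item 5, read literally | not a crossover | crossover |
| 4.1 | crossover | not a crossover |
| 2.7.2, as-treated | moved to exercise group | stays in arthroscopy group |
| 2.7.2, per-protocol | excluded | kept in arthroscopy group |

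Item 5 uses nearly the same wording that 2.7.2 uses to keep a patient in the arthroscopy per-protocol set, so it looks like text carried over from there. If x of N operated arthroscopy-arm patients reached 19 sessions, 4.1 reports x crossovers and item 5 reports N − x. The patients named are entirely different, and the totals agree only if x = N/2. The result does not depend on where the threshold lies.

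**2. The 80% label**

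Inputs from 2.4: denominator 24 sessions, stated cut-off 19 sessions, stated percentage 80%.

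- 0.80 × 24 = 19.2. The plan's 19 is reproduced only by rounding this to the nearest whole session.
- 19/24 = 79.2%, which is below 80%.
- 20/24 = 83.3%, so 20 is the smallest whole number that is literally at least 80%.

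**3. Each count under both readings**

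| Sessions | Share of 24 | Band by count (2.4) | Band by printed percentage |
|---|---|---|---|
| 18 | 75.0% | Poor | Poor |
| 19 | 79.2% | Satisfactory | Poor |
| 20 | 83.3% | Satisfactory | Satisfactory |
| 23 | 95.8% | Satisfactory | Satisfactory |
| 24 | 100.0% | Excellent | Satisfactory |
| 25 | 104.2% | Excellent | Excellent |

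The two readings part only at 19 and at 24. At 19, an exercise-arm patient has completed treatment by count but not by percentage. An arthroscopy-arm patient with 19 postoperative sessions is a crossover by count but not by percentage. At 24, the Excellent label of more than 100% is not met, and the printed Satisfactory range includes 100%.

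**4. Which reading is intended**

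Every place that states a count (2.4, 2.7.2, 4.1 and the Figure 2 legend) puts the line between 18 and 19. None states 20.

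**The case against.** The strongest reply is that the plan already gives one usable rule. The percentage-only completion rule in 2.4 comes directly after 18 or fewer sessions has been equated with less than 80%. In the crossover and arthroscopy-arm wording, more than 80% is followed by the count. Section 2.7.2 itself converts the exercise-arm 80% into fewer than 19 sessions. This stands. A reader might infer that the cut-off changes between sections, so that the same patient completes treatment in one and not in another. The document does not support that: the conflict is between a rounded percentage and a constant count.

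A reader might also infer that the 79.2% arithmetic produces the crossover contradiction. It does not, because item 5 would be wrong at any threshold.

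It can also be said that 4.1 is affirmative and clear while item 5 is barely grammatical, so nobody would follow item 5. That makes the error less likely to reach the tables. It does not make item 5 right, since item 5 is the entry in the list of variables to be presented.

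On the 24-session point, the split between the top two bands is descriptive and defines no analysis population. The Table 3 rows are also partly broken in the text available here. Both remarks are fair, but the text of 2.4 shows the mislabel by itself.

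Finally, a reader might attach a number of misclassified patients. If 2% to 5% of about 70 patients per arm (140 split equally) had exactly 19 sessions, that would be 0.02 × 70 = 1.4 to 0.05 × 70 = 3.5 patients. Both the share and the equal split are assumptions; the SAP gives no session distribution. The figure would matter only if the percentage overrode the stated count.

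**Conclusion.** The crossover definition in 2.4 item 5 contradicts 4.1 and 2.7.2 and should be corrected. Read literally, it reverses the status of every operated arthroscopy-arm patient in the Table 3 crossover rows and in the adverse-event grouping. The as-treated and per-protocol sets have their own wording in 2.7.2 and do not inherit this error.

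The percentage labels are inexact: 19 sessions is 79.2%, and 24 sessions is exactly 100%. The first is a rounding label that can affect only patients with exactly 19 sessions, through treatment completion and the per-protocol and as-treated analyses of secondary outcomes. The second affects only how patients with exactly 24 sessions are described in Table 3. How many patients sit at either value cannot be determined from the SAP.

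An effect on the main result is not supported. The primary analysis in 2.7.1 and 5.1 is intention-to-treat on all randomized patients, and the sample size in 3.1 uses none of these definitions. The conclusion that 19 is the intended count rests on its use wherever the plan gives a count.

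**What to change.** - State the arthroscopy-to-exercise crossover definition once, affirmatively, and reconcile 2.4 item 5 with 4.1 and 2.7.2 by referring to that single statement. Redirect the cross-reference in 2.4 item 6 to it.
- Express treatment completion and per-protocol and as-treated membership by the session count already in use, 19 or more versus 18 or fewer. Where 80% is kept, mark it as approximate (19/24 = 79%).
- Relabel the bands in 2.4 and Table 3 as 24 or more, 19–23, and 18 or fewer.
- Do not move the cut-off to 20 to make the percentage exact. Section 2 says the 24-month follow-up was finalized in December 2014, so that would change population membership after follow-up closed, merely to repair a rounding label.

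The cost is a few lines of SAP text and one derivation rule. No new data are needed, and the primary analysis does not change.

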## **2.5. Economic Evaluation**

The EQ-5D will be applied in a health economic evaluation. This will not be a part of the 2-year follow-up of this trial but is planned for the 5-year follow-up and will be published in a separate paper.

#### 2.6. Radiographic Evaluation

One of the inclusion criteria in this RCT is osteoarthritis evaluated according to KL in a fixed-flexion posterior-anterior radiography. This procedure will be repeated in the 5-year follow-up and results will be published in a separate paper. Radiography is not performed in the 2-yeas follow-up.

## 2.7. Specification of Endpoints

#### 2.7.1. Primary Endpoint

The trial is designed as a superiority trial, i.e. we expect that one of the treatment groups will improve more than the other group in the primary outcome  $KOOS_4$  from baseline to the primary endpoint after 2 years. Thereby, the primary endpoint is based upon the between-group difference in change in  $KOOS_4$ .

The primary analysis of the primary outcome (KOOS4) will be analyzed in an intention-totreat (ITT) analysis. It implies that for all patients randomized to one treatment, should be analyzed according to the treatment to which the patient was allocated, irrespective of whether they received this or some other treatment, or no treatment at all (Figure 2). The purpose of this ITT principle is to preserve the theoretical basis for the validity of the statistical results, specifically by eliminating the possibility that patients with known or unknown prognostic factors are systematically selected to a treatment.

The *ITT population* is equal to all patients randomized to the two treatment arms, and the dataset is equal to the "all patients randomized set" (APRS).

Missing values due to patients' absence from follow-ups or withdrawal from the study are not uncommon in clinical trials. Several approaches are described for handling missing data in the ITT analysis, and among them "last observation carried forward" (LOCF) (the last observed outcome is regarded as the final outcome), multiple imputation (MI) (stochastic technique which depends on model-based imputation of multiple values for each missing observation) and mixed model (MM) analysis. A MM analysis includes all patients with at least one baseline or follow-up value, and includes both fixed and random factors. The MM method is shown to have higher statistical precision in analyzing data from an RCT, than LOCF or MI methods. Therefore, MM method is chosen for the analysis of the primary outcome in this trial.

Treatment effect will be determined as difference between groups in change in the primary outcome KOOS4 from baseline to the 2-year follow-up. Since KOOS contains the full and original version of the Western Ontario and McMaster Universities Osteoarthritis Index (WOMAC), it has been usual to apply a minimal important change (MIC) of 10 points, which has been demonstrated for WOMAC. Recent studies in OA patient populations have applied a MIC of 15%. However, percentage change from baseline is not recommended as an outcome in controlled trials, since it has low statistical power, is highly sensitive to changes in variance and fails to protect from bias in the case of baseline imbalance.

We acknowledge that MIC is dependent on context factors such as population, intervention, and time to follow-up. In this trial, a possible bias may be a result of the different interventions (see section 2.1.) and this may affect the scores in the different KOOS subscales different in the two treatment groups, and thereby the change in KOOS4 may differ in the two groups as a result of the bias alone. Therefore, in the between-group analyses, the MIC is dubious and of poor value. On the contrary, in the within-group analyses, it is still reasonable to assess a 10-point difference as MIC.

Superiority will be tested using the two-sided 95% confidence interval (CI) of the mean change in  $KOOS_4$  between the two treatment groups.

# 2.7.2. Secondary Endpoints

Secondary endpoints will be analyzed for between- and within-group differences using ITT, PP (per protocol) and AT (as treated) analyses (see sections 2.7.1 and 5.2.)(Figure 2).

The *PP population* will be defined as the following:

In the arthroscopy group, included patients are: All patients randomized to arthroscopy that went through surgery, and not have had postoperative active physiotherapy (exercises) more than 80 % of twice a week in 12 weeks (19 or more sessions)(equivalent to 80 % in the exercise group), are included.

In the exercise group patients who participated in the program with at least 80 % compliance during the 12 weeks intervention period and did not cross over to the surgical treatment arm during the 2 years period and not have had any other surgery to the index knee (osteotomy, arthroplasty) within two years, are included.

This means that the following will be excluded from the PP analysis:

- 1) Those who were randomized to arthroscopy
  - a. but never went through surgery
  - b. but had postoperative exercise therapy supervised by physiotherapists (defined as 19 or more sessions )
- 2) Those who were randomized to exercise therapy supervised by physiotherapist
  - a. but never went through exercise or participated in less than 19 sessions ( 80 % of the minimum of 24 exercise sessions)
  - b. but crossed over to the surgical treatment arm within 2 years

The AT population will be defined as the following:

In the arthroscopy group, included patients are: All patients randomized to arthroscopy that went through surgery, and not have had postoperative active physiotherapy (exercises) more than 80 % of twice a week in 12 weeks (19 or more sessions)(equivalent to 80 % in the exercise group), are included. Additionally; Patients from the exercise group that within 2 years crossed over to surgery, are included in the arthroscopy group.

In the exercise group patients who participated in the program with at least 80 % compliance

during the 12 weeks intervention period and did not cross over to the surgical treatment arm during the 2 years period and not have had any other surgery to the index knee (osteotomy, arthroplasty) within two years, are included. Additionally; patients from the arthroscopy group that within two years crossed over to exercise (performed more than 80 % of twice a week in 12 weeks (19 or more sessions), are included in the exercise group.

The KOOS subscales Pain, Symptoms, ADL, Sport/Rec and QOL, EQ- 5D Index, EQ-5 VAS, weight and global knee function will be presented as mean (with 95% CI) for each treatment group. Between-group differences in change from baseline to 2 years will be statistically assessed. Each subscale of the KOOS will be presented graphically for its development over the 2 years period.

All issues during the trial found in the treatment records from the project physiotherapist, hospital records or the questionnaire from the follow-ups will be assessed to determine whether it represents an AE or not. AE will be presented in a table (see Table 1) and analyzed statistically by comparing actual numbers of serious AE (site other than index knee, index knee and all serious events) and non-serious AE (site other than index knee, index knee and all serious events).

AE associated with surgery will be given in Table 1 for the following groups:

1. Those receiving arthroscopic meniscal resection by randomization

2. All treatment dependent AE reported during and after surgery in those who had surgery even though randomized to the exercise therapy throughout the follow up period

AE associated with exercise therapy will be given in Table 1 for the following groups:

1. Those remaining in the 'Exercise therapy' group throughout the follow up period

2. All treatment dependent AE reported prior to the surgery in those who had surgery even though randomized to the exercise therapy

3. Those randomized to surgery but crossing over to exercise during the follow-up period

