#### 3.2. Randomization and Blinding

The schedule for randomization was randomly generated using a computer before the initiation of the trial. To conceal the outcomes of the randomization, the allocation numbers were put in concealed, opaque C5 envelopes. An independent staff member prepared the envelopes. These were kept in a locked location accessible only by one research assistant. Following the informed consent and completion of the baseline measures, the envelopes were opened by the patients and the allocation was revealed.

The randomization was stratified for gender, to ensure equal gender distribution in the two groups. In both genders there were used block randomization with blocks of eight.

The randomization was not stratified for center, because initially the trial was planned to be finalized in one hospital only; the Oslo University Hospital (OUH). Due to less patient flow than suspected, the recruitment was after patient number 53 taken over by Martina Hansens Hospital (MHH). The recruitment started at OUH in October 2009 and continued after patient number 54 at MHH from May 2011 and finished (patient number 140) in September 2012.

All patients went through baseline and follow-up tests at NIMI (Norsk Idrettsmedisinsk Institutt), Ullevål, Oslo. Patients randomized to arthroscopy were treated in the respective hospital that they were recruited from, and patients randomized to exercise therapy went through the interventions at NIMI (patients recruited between patient number 1 and 83) or at Gnist Trening og Fysioterapi, Bærum, an external physiotherapist institute.

Equality in patient treatment in the two interventional hospitals and two physiotherapist institutes respectively, was considered extremely important, especially on account of the lack of randomization stratification for center. Similarity in the recruitment and treatment procedures was ensured by written procedures and protocols and head-to-head instructions and dialogues. Only one surgeon was involved in recruiting at OUS, and another one at MHH. Fifty-four out of the total 64 (84 %) surgical procedures were performed by these two surgeons. Equivalently, the exercise therapy was performed by one dedicated physiotherapist in each institute, following similar procedures and protocols.

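### The as-treated definition carries over the per-protocol 80% compliance filter, so on the readable text non-operated patients with fewer than 19 exercise sessions belong to no as-treated group

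*SAP*

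**What the plan says.** Section 2.7.2 of the SAP builds the AT population from four entry routes.

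1. Arthroscopy group, own arm: "All patients randomized to arthroscopy that went through surgery, and not have had postoperative active physiotherapy (exercises) more than 80" per cent of the twice-weekly programme, which the SAP sets at 19 sessions.
2. Arthroscopy group, added: "Additionally; Patients from the exercise group that within 2 years crossed over to surgery, are included in the arthroscopy group". No number of sessions is required.
3. Exercise group, own arm: "In the exercise group patients who participated in the program with at least 80 % compliance", with no crossover and no other surgery on the index knee within two years.
4. Exercise group, added: "patients from the arthroscopy group that within two years crossed over to exercise", again defined by 19 or more sessions.

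Routes 1 and 3 repeat the PP definition in the same section. The patients at issue are foreseen there: the PP exclusions name arthroscopy-arm patients who were not operated, and exercise-arm patients in the class "but never went through exercise or participated in less than 19 sessions". Section 2.4 adds: "Less than 80 % compliance is defined as not completed treatment allocation". PP has a list of exclusions. AT has neither such a list nor a category for patients who received neither treatment.

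Section 5.2 limits PP and AT to a range of secondary outcomes. The primary analysis (sections 2.7.1 and 5.1) is by intention to treat in all randomised patients.

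**The concern.** An as-treated analysis is expected to place patients by the treatment they received. Here the non-operated side is restricted to patients who completed the programme, while the operated side takes every exercise-arm crossover, completer or not. Whether an exercise-arm non-completer is analysed at all therefore depends on a later event, and section 4.1 ties that event to symptoms: patients who worsened or did not improve were reassessed, and surgery was decided on history and examination.

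Non-completers may have stopped because exercise did not help or because they recovered early. In either case the exercise mean describes completers only. The SAP itself recalls (section 2.1) a cited trial in which the Symptoms subscale showed no significant difference per protocol but one in favour of surgery as treated, so the definition of the population can alter what is concluded.

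**Working it through.** **Inputs.** From the SAP: 140 randomised (section 1); gender-stratified blocks of eight and "Fifty-four out of the total 64 (84 %) surgical procedures were performed by these two surgeons" (section 3.2); SD 15 (section 3.1). The SD belongs to the sample-size calculation, which reproduces: 2 × 15²/10² × 10.5 = 47.25, so 48 per group. It is borrowed here for scale. The SAP gives no AT sample size, poor-compliance rate or crossover rate. Assumed for illustration: 70 per arm, 5–30% of the exercise arm below 19 sessions, 20% crossover, non-completers 10 points worse, and no dropout.

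**Step 1: follow each path through the text.**

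| Arm | Arthroscopic surgery | Sessions | AT group |
|---|---|---|---|
| Exercise | no | 19 or more | exercise |
| Exercise | no | fewer than 19 | none |
| Exercise | within 2 years | any | arthroscopy |
| Arthroscopy | no | 19 or more | exercise |
| Arthroscopy | no | fewer than 19 | none |
| Arthroscopy | yes | fewer than 19 | arthroscopy |
| Arthroscopy | yes | 19 or more | exercise |

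Splitting further by other index-knee surgery gives 16 combinations, of which 5 have no group. Four are the two rows marked none. The fifth, an exercise completer with other index-knee surgery, is a separate matter. Step 1 needs no assumption: a patient with 18 of 24 sessions (75%) and no surgery is in no group.

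**Step 2: how many patients.** With 70 per arm and 64 procedures in total, at least 70 − 64 = 6 arthroscopy patients were never operated, and more if the 64 include crossover operations. Since 140 = 17 × 8 + 4, incomplete blocks in two strata allow an arm difference of at most 4, so arms of 68–72 and a minimum of 4 to 8. Their session counts are unknown. If all 6 had fewer than 19 sessions, the share without a group is (70 × f × 0.80 + 6)/140, where f is the poor-compliance rate:

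- f = 5%: 8.8/140 = 6.3%
- f = 10%: 11.6/140 = 8.3%
- f = 20%: 17.2/140 = 12.3%
- f = 30%: 22.8/140 = 16.3%

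**Step 3: distance between the two rules.** Restoring non-operated exercise-arm non-completers leaves the arthroscopy group unchanged. The AT difference therefore moves by (their share of the non-operated exercise arm) × (gap). With crossover unrelated to compliance that share is f, so a 10-point gap gives 0.5, 1.0, 2.0 and 3.0 points at 5, 10, 20 and 30%.

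**Step 4: which rule is nearer the truth.** Take no true effect and f = 20%: 14 non-completers and 14 crossovers in the exercise arm, 64 operated in the arthroscopy arm. Differences are arthroscopy minus exercise.

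- *Poor prognosis balanced by randomisation, crossover independent of it.* The operated mean is 0.20 × (−10) = −2.0. As written: −2.0 − 0 = −2.0. Repaired: −2.0 − (−2.0) = 0.0.
- *Every crossover is a non-completer.* The operated mean is (64 × (−2) + 14 × (−10))/78 = −3.4. No non-operated non-completers remain, so both rules give −3.4.
- *No crossover is a non-completer.* The operated mean is −128/78 = −1.6. As written: −1.6. Repaired: −1.64 + 140/56 = +0.9.
- *Non-completers worse in the exercise arm only, crossover independent.* As written: 2.8 × (−10)/78 = −0.4. Repaired: −0.36 + 112/56 = +1.6.

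A simulation with balanced prognosis and crossover made more likely by a poor score gave about −5.8 as written and −3.9 repaired. Those values depend on the assumed strength of that link.

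**Step 5: precision at f = 20%.** As written: 15 × √(1/78 + 1/44.8) = 2.81. Repaired: 15 × √(1/78 + 1/56) = 2.63. The written rule has a standard error about 7% larger (2.81/2.63), or about 10% (2.81/2.55) if the 6 arthroscopy patients are also placed with the non-operated.

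**The case against.** The strongest reply is that the omission is coherent. Section 2.4 treats fewer than 80% of sessions as treatment not completed, so a patient with neither surgery nor a completed programme had neither treatment as defined and may be left out of a two-treatment comparison. This stands for arthroscopy-arm patients with no surgery and little or no exercise. Putting them in the exercise group is debatable, and they need a label of their own. It is weaker for exercise-arm patients who did part of the programme, and the AT text does not state such an exclusion.

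Second, in the last hand-worked case of step 4 the written rule lies nearer zero (−0.4 against +1.6). That case makes non-completion harmful in one arm only. With prognosis balanced by randomisation the order reverses. Neither model is established by the SAP, so the direction and size of bias remain open.

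Third, any as-treated analysis sorts patients by events after randomisation. That stands: the repair does not remove confounding by symptom-driven surgery. It removes an additional filter applied to one side.

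Fourth, Figure 2 shows the analysed groups and is not available. Its footnote separates patients below and above the cut-off, so it may place these patients. The written definition should still do so, because section 7 makes the SAP the statistician's work description.

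A reader might also infer that non-completers in both arms are kept once operated. The text supports this asymmetry for the exercise arm only: an arthroscopy-arm patient operated later has simply received the allocated treatment.

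**Conclusion.** The point holds as a defect of definition in a supportive analysis. On the readable text, non-operated patients below 19 sessions have no AT group, and exercise-arm non-completers are retained only through surgery. The resulting contrast can be biased and is less precise than it need be.

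The size cannot be derived from the SAP. The illustrations (6–16% of patients without a group, 0.5–3 points between the rules, a standard error about 7–10% larger at 20% poor compliance) rest on assumed compliance, crossover and outcome gaps. They should not be read as an estimate of bias in this trial. Nor does the SAP support reading this as a threat to the main result: the primary intention-to-treat analysis keeps all randomised patients. The change should be made before unblinding because it is cheap and the set is prespecified.

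**What to change.** In section 2.7.2:

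- Remove the 19-session condition for non-operated exercise-arm patients from the AT definition, so that all of them are analysed in an exercise/non-operative group. Keep the 19-session criterion for PP.
- List arthroscopy-arm patients with neither surgery nor 19 sessions explicitly, with counts, as a labelled 'neither treatment' category. A sensitivity analysis may place them in the non-operative group.
- Report the completers-only version, as now written, as a sensitivity analysis.
- Bring Figure 2 into line with the revised text.

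The cost is wording and one or two extra analyses, with no new data. The downside is small: the AT contrast moves towards surgery versus non-operative management that includes partial exercise. The compliance rows of Table 3 already describe how much exercise was done.
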